This study aimed to examine the effects of self-administered acupressure at the Shenmen (HT7) and Neiguan (PC6) points on emotional distress, anxiety, depression, stress, work-related fatigue, and resilience among clinical nurses.

Methods

This study adopted a single-blind randomized controlled trial (RCT) design. It was approved by the Institutional Review Board of a medical center (IRB No. 24-CT6-13) and registered at ClinicalTrials.gov (NCT06946888). The study was conducted from June 13, 2024, to September 22, 2024. Participants included nurses aged 20 and above working in clinical departments. Exclusion criteria included: (1) refusal or inability to comply with the study; (2) non-clinical roles (e.g., administrative units, supply departments); and (3) pregnancy. Out of 463 screened nurses, 160 were eligible based on the Brief Symptom Rating Scale (BSRS-5 ≥ 4) or Distress Thermometer score ≥ 3 and agreed to participate. They were randomly assigned via computer to the intervention group (n=80) or control group (n=80).

Interventions

Participants in the intervention group received in-person instruction from a trained research assistant on how to self-administer acupressure targeting two specific acupoints on each hand—Shenmen (HT7) and Neiguan (PC6)—**resulting in a total of four acupoints (two on each hand)**. Participants were guided to apply approximately 3 kg of thumb pressure to each acupoint until a sensation of soreness or tingling was perceived. Each acupoint was stimulated with 15 rhythmic presses (approximately 30 seconds per point), totaling about 2 minutes per session for all four acupoints. The intervention was performed **twice daily for two consecutive weeks**, and participants were provided with illustrated instructions (Figure 1) and a daily acupressure log to record adherence. The **control group** received no intervention. **Although the intervention lasted 2 weeks, all participants in both groups were followed for 8 weeks and completed weekly questionnaires throughout the follow-up period.**

[figure not shown]

Figure 1. Anatomical locations of Shenmen (HT7) and Neiguan (PC6) acupoints.

HT7 (Shenmen) is located at the wrist crease on the radial side of the flexor carpi ulnaris tendon.

PC6 (Neiguan) is found approximately two cun (about three finger-widths) proximal to the wrist crease, between the palmaris longus and flexor carpi radialis tendons.

Instruments

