All statistical analyses were conducted using IBM SPSS Statistics version 30.0. Continuous variables were summarized as mean \pm standard deviation (SD), and categorical variables as n (%). Baseline group comparability was assessed using independent-samples t tests (continuous variables) and χ^2 tests (categorical variables). Variables that differed significantly at baseline ($p < .05$) were considered potential confounders; because age differed significantly between groups, it was included as a covariate in all longitudinal models.

Within-group changes from baseline (weeks 0–8) were examined using paired t tests. Between-group comparisons at each follow-up time point were performed using independent-samples t tests. For significant between-group differences, effect sizes were calculated using Cohen’s d with 95% confidence intervals (CI), where 0.2, 0.5, and 0.8 indicated small, medium, and large effects, respectively.

To assess the longitudinal effects of the intervention, generalized estimating equations (GEE) were applied with a normal distribution, identity link, and an exchangeable correlation structure. The model included group (intervention vs. control), week (categorical: 0–8), the group \times week interaction, and age as a covariate. Robust (sandwich) standard errors were used. Regression coefficients (B), standard errors, Wald χ^2 statistics, 95% CIs, and p values for group \times week contrasts are reported. GEE was chosen over repeated-measures ANOVA or generalized linear mixed models because it provides population-averaged estimates, is robust to correlation misspecification, accommodates missing data under MAR/MCAR assumptions, and does not require sphericity. All tests were two-tailed with $\alpha = .05$.

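### Neither the weekly t tests nor the GEE adjusts for the outcome's week-0 score; with complete data this costs precision, not validity, and the remedy needs no new data

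*Combined protocol and SAP*

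**What the plan says.** All of the analysis text is in the Statistical Analysis section. The weekly comparison of the arms is unadjusted: "Between-group comparisons at each follow-up time point were performed using independent-samples t tests". The next sentence makes the standardised effect size conditional: "For significant between-group differences, effect sizes were calculated using" Cohen's d with a 95% CI.

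The longitudinal analysis is a GEE. Its specification is "The model included group (intervention vs. control), week (categorical: 0–8), the group" by week interaction, plus age. Week 0 is thus one of the nine response occasions, and each arm has its own week-0 mean. The equations "were applied with a normal distribution, identity link, and an exchangeable correlation structure", with robust standard errors. Age is there because of a baseline significance test: "because age differed significantly between groups, it was included as a covariate in all longitudinal models". The section also says that coefficients, standard errors, Wald statistics, 95% CIs and p values for the group-by-week contrasts are reported, and it attaches no significance condition to them.

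Otherwise, the week-0 score is used explicitly only in the within-arm paired t tests. The Methods section gives the allocation ("They were randomly assigned via computer to the intervention group (n=80) or control group (n=80") and the dates ("The study was conducted from June 13, 2024, to September 22, 2024").

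**The concern.** In a randomised trial with a baseline measurement of the outcome, that measurement is usually among the strongest predictors of follow-up. Here no between-group analysis has it as a covariate. Covariates were chosen by whether the arms differed at baseline with p < .05, not by how well a variable predicts the outcome.

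The two analyses miss it in opposite ways. The t test gives the week-0 score a weight of zero. The GEE contrast subtracts the whole of it, a weight of one. The best linear weight is the regression slope of follow-up on baseline, which usually lies between the two. With equal SDs that slope is r, so a chance week-0 imbalance of D moves the t-test estimate by rD and the change contrast by -(1 - r)D. Covariate adjustment removes both.

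At stake are wider intervals and lower power than the collected data allow, across weekly comparisons on several scales.

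**Working it through.** **Inputs from the documents.** 80 per arm (Methods); two-sided alpha .05; the analysis specifications above. The plan states no sample-size calculation, target effect, SD or baseline-to-follow-up correlation, so there is no figure of its own to reproduce.

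**Assumptions.** Complete data; week 0 as GEE reference; t tests on raw follow-up scores; true effect 0.4 follow-up SD; r = 0.4 to 0.7; k = week-0 SD divided by follow-up SD = 0.8, 1.0 or 1.2.

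**Step 1: what the GEE contrast is.** Each arm has a free mean at each week, so with complete data the group-by-week contrast is the difference between arms in mean change from week 0. Age enters as a main effect with one slope for all weeks, so it cancels from a within-person change. In simulated complete data sets the stated GEE's week-8 contrast equalled the difference in mean change to rounding error (largest gap about 4e-16). It was also the same with and without age when age was imbalanced and predictive.

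**Step 2: variances**, in units of 2 SD²/80 with the follow-up SD:

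- t test: 1
- GEE contrast: 1 + k² - 2rk
- baseline-adjusted: 1 - r²

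Relative to the adjusted analysis, the t test is therefore 1/(1 - r²). Since 1 + k² - 2rk = (1 - r²) + (k - r)², the GEE contrast is 1 + (k - r)²/(1 - r²).

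Example at r = 0.4: t test 1/0.84 = 1.19; GEE with k = 1, 1 + 0.36/0.84 = 1.43.

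| Variance ratio to adjusted | r = 0.4 | 0.5 | 0.6 | 0.7 |
|---|---|---|---|---|
| t test, any k | 1.19 | 1.33 | 1.56 | 1.96 |
| GEE, k = 0.8 | 1.19 | 1.12 | 1.06 | 1.02 |
| GEE, k = 1.0 | 1.43 | 1.33 | 1.25 | 1.18 |
| GEE, k = 1.2 | 1.76 | 1.65 | 1.56 | 1.49 |

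The GEE loss depends on the gap between k and r. It is negligible when they are close, but neither a high r nor a narrow week-0 SD is enough alone: r = 0.8, k = 1.2 gives 1 + 0.16/0.36 = 1.44, and r = 0.3, k = 0.8 gives 1 + 0.25/0.91 = 1.27.

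**Step 3: power** at 0.4 SD, noncentral t with 158 df (157 adjusted):

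| Power, % | r = 0.4 | 0.5 | 0.6 | 0.7 |
|---|---|---|---|---|
| t test | 71 | 71 | 71 | 71 |
| Adjusted | 78 | 83 | 88 | 94 |
| GEE, k = 0.8 | 71 | 78 | 86 | 94 |
| GEE, k = 1.0 | 63 | 71 | 80 | 90 |
| GEE, k = 1.2 | 54 | 62 | 71 | 82 |

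The 95% CI half-width is 0.31 SD for the t test, against 0.29, 0.27, 0.25 and 0.22 adjusted.

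**Step 4: validity and direct fits.** With no true effect, simulated rejection rates were near 5% (t test 4.4%, change 4.9% and adjusted 4.6% in 4000 runs at r = 0.5; stated GEE 4.0% and 4.3% in 300 runs each at r = 0.3 and 0.6). Direct fits of nine-week data with a true effect of 0.4 (400 trials per setting) gave mean estimates of 0.395 to 0.409. Week-8 power for t test, stated GEE and adjusted GEE was 72/65/78% at r = 0.4, k = 1 and 70/93/97% at r = 0.7, k = 1. The loss is in precision, not bias.

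**The case against.** The strongest reply is that this is a preference between valid analyses. The GEE is the analysis meant to assess the longitudinal effect and it does use week 0. The loss rests wholly on an assumed r and k; at r = 0.7 and k = 0.8 the stated GEE and the adjusted analysis both have 94% power. The study is finished, so the planned tests can gain nothing. All of this stands, and it is why the point is minor. It does not remove the point, because the t tests lose precision at any non-zero r.

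Three stronger readings are tempting.

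- *That t-test power decides at which weeks any effect estimate is shown.* The section does not support this. The GEE contrasts and their 95% CIs are reported without a significance condition; only Cohen's d appears tied to a significant t test. That restriction is a separate reporting problem. Baseline adjustment with the same rule would still hide effect sizes, and reporting d at every week would cure it without any covariate.
- *That the results are biased or the type I error is wrong.* With complete data neither follows under randomisation. With missing data the assurance lapses: in one assumed scenario (no effect, r = 0.6, dropout in the intervention arm only, driven by the week-0 score) the completers' t test was biased by -0.22 SD and rejected in 22% of runs, while the adjusted analysis and the GEE, whose working correlation was correct there, stayed near zero bias. The documents give no dropout figures, so nothing shows that this happened here.
- *That the age covariate does the work of baseline adjustment.* With complete data it drops out of the group-by-week contrast, and the t tests do not include it.

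**Conclusion.** The point holds as a free improvement of minor weight. That no between-group analysis has the week-0 score as a covariate follows from the text, as does the direction of the loss: any non-zero r for the t tests, any gap between k and r for the GEE contrast. The magnitude is conditional. For r of 0.4 to 0.7 and k of 0.8 to 1.2, variance is inflated by a factor of 1.19 to 1.96 for the t tests and 1.02 to 1.76 for the GEE contrast. At 0.4 SD this means 71% power for the t test and 54% to 94% for the GEE contrast, against 78% to 94% adjusted. The result also rests on complete data, raw scores in the t tests and week 0 as the reference week, none of which the documents state outright. It gives no ground for calling the planned analyses invalid.

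**What to change.** For each outcome, fit one longitudinal model with weeks 1 to 8 as the response and with baseline score by week, week, group by week and age as terms, using robust standard errors. Entering age by week is slightly better: complete-data estimates then do not depend on the working correlation, whereas with a single age slope they shifted by up to about 0.02 SD under an unstructured one. Report the adjusted group difference and 95% CI at every week, significant or not.

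If week 0 is instead kept as a response with a common mean in both arms, the exchangeable structure should be replaced by an unstructured one. With a pooled correlation p, the exchangeable variance factor is 1 + p² - 2pr; at assumed p = 0.68 and r = 0.4 this is 1 + 0.46 - 0.54 = 0.92, against 0.84 with the covariate. The covariate form is the simpler choice.

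Data collection is over, so show this as an openly labelled post hoc analysis beside the planned t tests and GEE, not in place of them. The week-0 scores are already in the GEE, so no new data are needed. The cost is one extra model per outcome, a few lines of SAP text and the disclosure. The rule that limits Cohen's d to significant differences needs its own correction.

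### Cohen's d is planned only for weekly comparisons that reach p < .05, so observed |d| below about 0.31 is never reported and the d shown for small true effects is inflated

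*Combined protocol and SAP*

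**What the plan says.** Four statements in the combined protocol and SAP fix the rule.

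- Statistical Analysis, on the weekly tests: "Between-group comparisons at each follow-up time point were performed using independent-samples t tests".
- The sentence that follows directly: "For significant between-group differences, effect sizes were calculated using" Cohen's d with 95% confidence intervals, "where 0.2, 0.5, and 0.8 indicated small, medium, and large effects, respectively".
- End of the same section, on the threshold: "All tests were two-tailed with" α = .05.
- Methods, on numbers: nurses were allocated to "the intervention group (n=80) or control group (n=80"). The Interventions section adds that both groups were "followed for 8 weeks and completed weekly questionnaires throughout the follow-up period".

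No d is planned for a comparison that misses .05. The section also plans GEE output: "Regression coefficients (B), standard errors, Wald χ^2 statistics, 95% CIs, and p values for group" × week contrasts, with no significance condition attached. Continuous variables are summarised as mean and SD, but the text does not say whether this is done by arm and week.

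**The concern.** An estimate that is reported only when its test is significant comes from a truncated distribution. Low observed values are removed, so the average of what remains lies further from zero than the truth. The 95% CI around a selected estimate no longer has its nominal coverage when the true effect is small.

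The rule would act many times. The Instruments section describes seven scales, or ten outcomes if the four burnout subscales are scored separately. Over eight follow-up weeks that is 7 × 8 = 56 to 10 × 8 = 80 gated comparisons. The table of d would have entries where p < .05 and blanks elsewhere. Acupressure lasts two weeks and follow-up eight, so whether an effect fades is a natural question, and small late effects are the ones most likely to be blank. The plan attaches its small, medium and large labels only to d, and d is the only planned measure comparable across scales that run from 0–10 to 0–100.

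This is separate from multiplicity. Adjusting the p values would leave the rule in place, and a stricter threshold would raise the cut-off for d.

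**Working it through.** The documents give no power calculation or target effect size, so there is no planned figure to reproduce first.

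**Inputs.** n = 80 per arm (Methods); independent-samples t test at each week, two-sided α = .05 (Statistical Analysis); benchmarks 0.2, 0.5 and 0.8 (Statistical Analysis). Assumptions: normal scores, equal variances, d based on the pooled SD, all 160 observed.

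**Step 1: smallest d that can be reported.** With equal arms, t = d × √(n/2), so significance requires

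|d| ≥ t(0.975, 2n − 2) × √(2/n) = 1.975 × √(2/80) = 1.975 × 0.1581 = 0.312.

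The documents give no dropout figure. If 72, 64 or 56 per arm were observed (assumed values), the cut-off would be 0.329, 0.350 or 0.375.

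**Step 2: what passes the filter.** One million noncentral-t draws per true d (158 df, noncentrality d × √40), keeping results with |t| > 1.975:

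| True d | Share significant | Mean reported \|d\| | Reported \|d\| below 0.5 | Reported \|d\| at or above 0.8 |
|---|---|---|---|---|
| 0 | 5% | 0.37 | 96% | 0.002% |
| 0.1 | 10% | 0.39 | 93% | 0.01% |
| 0.2 | 24% | 0.41 | 87% | 0.05% |
| 0.3 | 47% | 0.44 | 77% | 0.3% |
| 0.4 | 71% | 0.48 | 62% | 1% |
| 0.5 | 88% | 0.54 | 43% | 4% |
| 0.8 | 99.9% | 0.80 | 3% | 50% |

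The inflation is 0.41/0.20 ≈ 2.0-fold at a true d of 0.2, 0.44/0.30 ≈ 1.5-fold at 0.3 and 0.48/0.40 = 1.2-fold at 0.4. It has gone by 0.8. Without the filter, the mean d over the same draws is 0.20 at a true d of 0.2 and 0.50 at 0.5.

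**Step 3: coverage of the CI for d among significant results.** The standard error of d is √(2/n + d²/(4n)) and the interval is d ± 1.96 SE. A second simulation of one million draws per true d gives coverage of:

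- 0% at a true d of 0
- 69% at 0.1
- 89% at 0.2
- 95% at 0.3
- 96% at 0.4
- 97% at 0.5
- 95% at 0.8

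The loss is therefore confined to a true d of about 0.2 or less.

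**The case against.** The strongest reply is that the plan already reports unfiltered effect estimates. The GEE treats week as categorical from 0 to 8, so each follow-up week has a group × week contrast. Its coefficient, standard error and 95% CI are planned whatever the p value. These are age-adjusted and in scale units, and the plan assigns the longitudinal effect to this model, not to d. If means and SDs were tabulated by arm and week, a reader could also compute d.

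Most of this stands, and it limits the point. A reader might infer that the publication would show only inflated effects, or that the trial could not express uncertainty in weeks that miss .05. The documents do not support either reading, because the GEE coefficients and CIs cover those weeks.

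Two other inferences also go too far. One is that every reported d is selected to be large. The plan puts large at 0.8 and the cut-off is 0.31; at a true d of 0.2, 87% of the reported values lie below 0.5. The other is that small or null effects cannot appear. Only an observed |d| below about 0.31 is excluded. A true effect of zero still passes in 5% of tests and a true d of 0.2 in 24%, each time in exaggerated form.

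The GEE output does not repair the d values themselves. Its coefficients are in the units of each scale, so they cannot be compared across outcomes, and they carry no small, medium or large label. Recovering d from means and SDs depends on a table that the plan does not promise.

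**Conclusion.** The concern holds, limited to the standardised effect sizes. Under the stated rule, with 80 per arm, an observed |d| below about 0.31 is never reported, and reported values overstate small true effects, about twofold at a true d of 0.2. CI coverage after selection is poor at a true d of 0.1 or less, about 89% at 0.2, and not materially reduced from 0.3 upward.

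The inference from the GEE is unaffected. The defect is in one secondary measure, but it yields biased values and not merely missing detail, so it is worth correcting.

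The figures rest on normality, equal variances and complete data. Fewer observed nurses would raise the cut-off. They also take the significance in question to be that of the weekly t tests, which is the natural reading from the order of the sentences.

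**What to change.** Replace the sentence that makes Cohen's d conditional on significance with:

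> The between-group difference and Cohen's d, each with a 95% CI, are reported for every outcome at every follow-up week, whatever the p value.

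Preferably, derive d from the age-adjusted model difference so that it agrees with the GEE results. The cost is one sentence in the analysis section and more table rows: 56 to 80 entries on the count above, instead of only the significant ones. No new data are needed.

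### Seven outcomes are tested at up to eight weeks by two unranked analyses, all at .05, with no primary endpoint, primary week or multiplicity control; under assumed correlations a no-effect trial still gives at least one significant group difference about 54–97% of the time

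*Combined protocol and SAP*

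**What the plan says.** All of the testing rules are in the Statistical Analysis section of the combined protocol and SAP.

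- **Weekly t tests:** "Between-group comparisons at each follow-up time point were performed using independent-samples t tests". These are not adjusted for age or baseline.
- **GEE:** "To assess the longitudinal effects of the intervention, generalized estimating equations (GEE) were applied", with week as a nine-level factor. The model reports "95% CIs, and p values for group" × week contrasts. Age is a covariate "because age differed significantly between groups".
- **Error rule:** "All tests were two-tailed with" α = .05.
- **Effect sizes:** "For significant between-group differences, effect sizes were calculated using" Cohen's d with its 95% CI.

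The Background section lists seven outcomes, which match the seven instrument headings: the Distress Thermometer, BSRS-5, TDS, STAI-S, job stress, burnout and resilience. The Objective lists six constructs and ranks none. The title names psychological distress and depression but does not call either primary. The Interventions section adds: "Although the intervention lasted 2 weeks, all participants in both groups were followed for 8 weeks and completed weekly questionnaires throughout the follow-up period".

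**The concern.** Each outcome can be declared positive by either of two methods at any of up to eight weeks, and nothing says which result answers the trial's question. The two methods are not copies of each other. The t tests compare levels at a week, while the GEE contrasts compare change from week 0, so each adds its own chances of a false positive.

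The choice of week matters too. The intervention lasts two weeks and follow-up eight, and no section says whether a short-term or a lasting effect is the question. Under the plan as written, one favourable week on one scale from either analysis could be presented as the trial's result. The only standardised effect size is shown just for differences that passed .05, which makes a small true effect look larger than it is.

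**Working it through.** The plan gives no family-wise error rate, power or sample-size calculation, so there is no figure to reproduce.

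**Inputs from the documents:** 7 outcomes (Background, Instruments); up to 8 weekly follow-ups (Interventions); 80 per arm (Methods); two-sided .05 and two between-group analyses (Statistical Analysis).

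**Assumed, because the documents are silent:** every scale in every week; complete, normally distributed data; week correlation 0.5–0.8 exchangeable or 0.8–0.9 autoregressive; outcome correlation 0.3–0.9.

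**1. Count of tests.** 7 × 8 = 56 contrasts per method, and 2 × 56 = 112 for both. Burnout has four subscales, and the text does not say whether it is analysed as one score or four. With four there are 10 outcomes, so 10 × 8 = 80 per method. Within-group paired tests are left out.

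**2. Independence reference.** 1 − 0.95^56 = 94.3%, and 1 − 0.95^112 = 99.7%. The tests are correlated, so these are reference values only and are not used below.

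**3. Simulation under no effect.** Individual-level data were generated for weeks 0–8. The t tests compared levels at weeks 1–8. With complete data each GEE group × week contrast equals the difference between arms in mean change from baseline; direct exchangeable GEE fits with age and robust standard errors gave the same z values. Uncorrected sandwich errors were used, which adds slightly to the GEE figures. Chance of at least one p < .05, over the four week-correlation settings:

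| Outcomes counted | Outcome correlation | GEE alone | t tests alone | Both |
|---|---|---|---|---|
| Seven | 0.3–0.7 | 56–86% | 46–84% | 74–97% |
| Seven | 0.9 | 39–52% | 32–49% | 54–71% |
| Two named in the title | 0.3–0.9 | 27–47% | not tabulated | 40–66% |
| One | not applicable | 21–26% | not tabulated | 32–42% |

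At least one difference *favouring acupressure* (seven outcomes, both analyses) appears 44–74% of the time at outcome correlation 0.3–0.7 and 30–43% at 0.9.

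**4. Fewer weeks per scale.** With exchangeable week correlation 0.5–0.9, seven outcomes and both analyses, four tested weeks give about 45–85%, and one or two tested weeks about 22–66%.

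**5. Filtered Cohen's d.** The critical t on 158 df is 1.975. The smallest reportable d is 1.975 × √(2/80) = 0.312. For a true d of 0.2 the noncentrality is 0.2/0.158 = 1.26; it is significant 24% of the time, with mean reported d about 0.41. For a true d of 0.5 the figures are 88% and 0.54.

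**6. Candidate single tests.** The level is the first Holm step, .05/7 = .0071 (critical t 2.726 on 158 df). Take a true d of 0.4 in every week and exchangeable correlation 0.5.
- Mean of the eight contrasts: variance per person (1 + 7 × 0.5)/8 + 1 − 2 × 0.5 = 0.5625; SE √(2 × 0.5625/80) = 0.1186; noncentrality 0.4/0.1186 = 3.37; power 74%.
- Joint 8-df test: noncentrality 40 × 0.16 × (8 − 64/9)/0.5 = 11.38 on F(8, 151); power 34%.

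**7. Does the repair hold its level?** Under no effect, Holm over seven outcomes rejected at least once in 2–5% of trials for the averaged contrast (t, 158 df), 2–5% for the joint test with an F reference, and 4–10% for the joint test on chi-square. The joint test therefore needs a small-sample reference.

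**The case against.** **The GEE is plainly the main analysis.** It has a stated purpose, an age adjustment and a written rationale; the t tests have none of these. This is a fair reading, but the section never says that the GEE overrides the t tests. GEE alone still gives 39–86% for seven outcomes, so ranking the methods is not enough.

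**The title identifies the outcomes that matter.** It does not call them primary. Even one named outcome, without a named week, leaves four to five times the nominal 5% by GEE alone.

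**The size rests on assumptions.** This stands. A reader might infer that the trial's false-positive rate is known to exceed one half. The documents do not support that: they give no correlation between weeks or outcomes, and they say weekly questionnaires were completed without saying that every scale was in each one. The upper figures also count differences in either direction and by both methods.

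**Selective reporting.** A reader might infer that a favourable week was picked. The documents contain no between-group outcome results and do not show this. They show only that the plan would not prevent it. Nor is all reporting filtered by significance: GEE coefficients and confidence intervals are reported without that condition.

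**The data are already collected.** Also correct. A test chosen now cannot restore confirmatory error control, which is why the exploratory label has to come first.

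**Conclusion.** The concern holds and must be fixed. Followed as written, the .05 rule does not control the trial's overall error rate, and no other section supplies the missing hierarchy. The 54–97% (both analyses) and 39–86% (GEE alone) ranges are conditional on the assumed correlations and on weekly use of every scale. The direction does not depend on those choices: every setting examined is well above 5%, including one outcome alone and only one or two tested weeks per scale. The distortion of Cohen's d depends only on 80 per arm, normally distributed data and the significance filter.

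A reader might also infer that the averaged contrast is always the stronger test when an effect lasts. It is under the exchangeable settings but not under the autoregressive ones, so the test should be chosen by the question and not by a general claim about power.

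**What to change.** 1. If an earlier dated record (approved protocol or registration) names a primary outcome and week, use those. Otherwise label all results exploratory and the choice of test post hoc.
2. Declare the age-adjusted GEE the deciding between-group analysis, and the t tests and paired tests descriptive.
3. Use one GEE test per outcome, fixed before re-running, with Holm across all outcomes at .05. State whether burnout is one score or four. The test is either the mean of the eight group × week coefficients (if a sustained benefit is the question) or the joint 8-df group × week test with a small-sample reference (if the effect may fade). The joint test has no direction, so read direction from the adjusted differences. The plan relies on a GEE that "accommodates missing data under MAR/MCAR assumptions", so the small-sample correction must also suit incomplete data. Treat individual weeks as exploratory.
4. Report the adjusted difference, Cohen's d and 95% CI for every outcome and week, significant or not.

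**Cost.** Revised wording and a reanalysis of data already held. Fewer results can be called significant. Power at .05/7, with the first two rows for d = 0.4 in every week:

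| True effect | Week correlation | Averaged contrast | Joint test |
|---|---|---|---|
| Lasting | Exchangeable 0.5; 0.8 | 74%; over 99% | 34%; 90% |
| Lasting | Autoregressive 0.8; 0.9 | 56%; 81% | 58%; 95% |
| d = 0.4 in weeks 1–2 only | All four settings | 2–9% | 70% to nearly 100% |
| Straight line from 0.4 at week 1 to zero at week 8 | All four settings | 10–48% | 45–97% |

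For comparison, a single week's GEE contrast at an unadjusted .05 has about 72–98% power for d = 0.4 under the exchangeable settings.
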